11.2.2 CRF Retention

All information required by the Protocol will be collected on either CRF or source documents. Essential documents should be retained until the Sponsor informs the Investigator that documents are no longer need to be kept.

11.2.3 Record Maintenance

Regulation requires all investigators participating in clinical trials to maintain detailed clinical data for the duration of one of the following periods, whichever is shortest:

- (1) A period of at least two years following the approval date of an application for a marketing permit in support of which the results of the clinical investigation were submitted, or
- (2) A period of two years after the Sponsor notifies the Investigator that no further application is to be filed with the regulatory authority.

The Investigator will not dispose of any record relevant to this study without informing the Sponsor and providing an opportunity for the Sponsor personnel to collect such record. The Investigator shall take full responsibility for maintaining all documentation related to the conduct of this study, including subject records, research data, and pertinent correspondence. These documents are subject to inspection by the Sponsor and appropriate regulatory authorities.

3. LIST OF ABBREVIATIONS AND DEFINITION OF TERMS

ADHD	Attention-Deficit/Hyperactivity Disorder
ADHD-RS-IV	Attention-Deficit/Hyperactivity Disorder Rating Scale-IV
AE	Adverse event
BMI	Body Mass Index
	Conners' Adult Attention-Deficit/Hyperactivity Disorder Rating Scale-Self
CAARS-S:S	Report: Short Version
CGI-I	Clinical Global Impression- Improvement
CGI-S	Clinical Global Impression- Severity
CRO	Contract Research Organization
CS	Clinical Significance
C-SSRS	Columbia-Suicide Severity Rating Scale
DSM-5	The Diagnostic and Statistical Manual of Mental Disorders, Fifth Edition
	The Electrocardiogram (ECG) is a graphical recording of the cardiac cycle
ECG	produced by an electrocardiograph
E-SCT	Empirical-Sluggish Cognitive Tempo
HI	Hyperactivity-impulsivity
IQR	Interquartile Range
IA	Inattention
ITT	Intention-to-treat
LOCF	Last Observation Carried Forward
NCS	Non-Clinical Significance
PE	Physical Examination
PP	Per-protocol
PTAE	Pre-Treatment AE
SAEs	Serious Adverse Event(s).
SD	Standard Deviation
TEAE	Treatment AE

4. PROTOCOL AMENDMENTS

The version of approval protocol after enrolling the first subject was described as follow:

Approved date Approved by	Final (version:<protocol version>)	Amendment 01 (version:<protocol version>)
USFDA	2022/03/14 (Version 1.6)	2022/11/04 (Version 1.7)
TFDA	2022/04/18 (Version 1.6)	2022/11/09 (Version 1.7)
UCSF	2023/05/22 (Version 1.7)	
CGMH	2022/02/18 (Version 1.6)	2022/10/03 (Version 1.7)
CGHG	2022/04/18 (Version 1.6)	2022/10/28 (Version 1.7)
NTUH	2022/02/24 (Version 1.6)	2022/10/28 (Version 1.7)
TVGH	2022/04/12 (Version 1.6)	2022/11/03 (Version 1.7)

This protocol amendment about the statistical analysis is consisted of the following (compared to the final approved protocol)

Page	Version 1.6	Page	Version 1.7
37	None	39	**If the interval of visit 1 and visit 2 is within 7 days, Hematology and Blood chemistry test of visit 2 can be skipped.
38	None	40	Drug compliance is important for the safety and efficacy evaluations. Study coordinator needs to make sure drug adherence of the subjects is at least 80% during the treatment period. Otherwise, study coordinator(s) must report a protocol deviation including lower than 80% compliance and over 100% compliance during the treatment period.
44	Analyzing of Safety Parameters The data obtained before study drug administration in Visit 2 are set as baseline.	46	Analyzing of Safety Parameters The data obtained before study drug administration in Visit 2 or Visit 1 (if no data at Visit 2) are set as baseline.
44	The information of AEs contains characteristic, onset and duration,	46	The information of AEs contains characteristic, onset and duration, the

Page	Version 1.6	Page	Version 1.7
	frequency, the Investigator’s opinion of the relationship to the study drug (unrelated, unlikely, possibly, probably, definitely), outcome (recovered, recovered with residual effects, continuing, death, lost to follow-up) and severity.		Investigator’s opinion of the relationship to the study drug (unrelated, unlikely, possibly, probably, definitely), outcome (recovered, recovered with residual effects, continuing, death, lost to follow-up), therapy (no action, treatment given, withdrawn from study, temporarily discontinued) and severity.

5. INVESTIGATIONAL PLAN

5.1 Objective

5.1.1 Primary objective

The primary objective is to determine the effective doses and treatment period of PDC-1421 Capsule in subject with ADHD Rating Scale-IV (ADHD-RS-IV).

[figure not shown]
5.1.2 Secondary objective

The secondary objective is to determine the efficacy and safety profile of PDC-1421 Capsule in ADHD with ADHD-RS-IV, CAARS-S:S, E-SCT and CGI-I.

5.2 Study Design

This study is a double-blind, randomized, placebo-controlled, parallel-group study in patients with ADHD according to the Diagnosis and Statistical Manual of Mental Disorders, 5th Edition. At first stage, a number of 69 subjects will be randomly assigned on a 1:1:1 basis to one of the three arms (1 PDC-1421 Capsule plus 1 placebo TID, 2 PDC-1421 Capsules TID, 2 placebo TID) for 8 weeks and evaluated the safety and efficacy every two weeks during the treatment period. An interim analysis will be conducted to evaluate the efficacy of PDC-1421 and to decide whether it is necessary enter the second stage of Part II study in which 30 subjects will be randomly assigned on a 1:1:1 basis to one of the three treatment arms and receive the same treatment.

5.2.1 Schematic Diagram of Study

5.2.2 Study Medication Administration

Subjects will be assigned with a random number to be allocated into 3 treatment groups on a 1:1:1 basis and treated as following dose regimen:

- Placebo: 2 placebo capsules thrice daily after meal for 56 days (8 weeks).
- Low-Dose: 1 placebo capsule and 1 PDC-1421 Capsule (380 mg), thrice daily after meal for 56 days (8 weeks).
- High-Dose: 2 PDC-1421 Capsules thrice daily after meal for 56 days (8 weeks).

5.2.3 Flowchart of study procedures

	Screening	Treatment Period					Follow-up
Visit	1	2	3	4	5	6	7
*Week	-2 to 0	0	2	4	6	8	10
Informed consent	√						
Subject information	√						
Medical history	√						
DSM-5	√						
CAARS-S:S	√	√	√	√	√	√	√
CGI- S	√	√					
CGI- I			√	√	√	√	√
ADHD-RS-IV	√	√	√	√	√	√	√
E-SCT	√	√	√	√	√	√	√
C-SSRS	√	√	√	√	√	√	√
Concomitant medication	√	√	√	√	√	√	√
Physical examination						√	
Vital sign	√	√	√	√	√	√	√
ECG	√					√	
Laboratory examination							
Pregnancy test	√						√
**Hematology	√	√		√		√	
**Blood chemistry	√	√		√		√	
Eligibility evaluation	√						
Drug accountability		√	√	√	√	√	
AE/SAE evaluation		√	√	√	√	√	√

*On ±2 days.

** If the interval of visit 1 and visit 2 is within 7 days, Hematology and Blood chemistry test of visit 2 can be skipped.

5.3 Statistical Methods Planned in the Protocol and Determination of Sample Size

5.3.1 Populations for Analysis

The INTENT-TO-TREAT (ITT) POPULATION consists of all randomized subjects who receive at least one dose of study medication and fulfill all inclusion, exclusion criteria and have any post-baseline safety data collected.

The PER-PROTOCOL (PP) POPULATION is defined as (1) The drug compliance is at least 80% (2) Subjects have completed data to determine the primary endpoint. (3) Subjects cannot have protocol deviation. The protocol deviation will be defined as (1) Inclusion or exclusion criteria not satisfied. (2) Not permitted concomitant medications (3) Wrong randomized treatment prescribed.

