8.3 Analysis of Efficacy and Safety

The efficacy measures are conducted on the per-protocol (PP) and intent-to-treat (ITT) basis. The per protocol will be defined as (1) The drug compliance is at least 80% (2) Subjects have completed data to determine the primary endpoint. (3) Subjects cannot have major protocol deviation. The major protocol deviation will be defined as (1) Inclusion or exclusion criteria not satisfied. (2) Not permitted concomitant medications (3) Wrong randomized treatment prescribed. An intent-to-treat (ITT) basis will be defined as the data are analyzed by the treatment groups to which the randomized patients who take at least one dose of study medication and have any post-baseline safety data collected. The safety measures are conducted on the patients who take at least one dose of study medication. The data are analyzed utilizing the last observation carried forward (LOCF) technique to impute the missing data.

The efficacy and safety information recorded on CRF will be summarized by tables presented in frequency and percentage for categorical variables, in mean with SD as well as median with the minimum and maximum for continuous variables. The comparison between three groups will be analyzed by nonparametric method as appropriate. All adverse events will be summarized with coding term, severity, relationship to study drug by frequency tables with the counts and percentage. In addition, serious adverse events will be listed with event narration.

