5.4 Changes in the Conduct of the Study or Planned Analyses

All the statistical analysis will follow protocolized statistical contents. However, due to the interim report results do not meet the requirement of protocol and the study was terminated, the chi-Square test and Wilcoxon signed-rank test between arms will not be performed.

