6.2 Data Sets Analyzed

Two study populations are intention-to-treat (ITT) population and per-protocol (PP) populations which are defined in section 5.3.1.

The efficacy evaluations will be performed on both of the ITT and PP datasets while the safety evaluations will be performed on the ITT dataset. The primary conclusion will be made for the primary endpoint on the ITT population. Demographic and baseline (Visit 2) characteristics will be performed on the ITT population.

Sample size, mean, 95% confidence interval of mean, median, standard deviation, inter-quartile range, maximum and minimum will be summarized for continuous variables. For categorical variables, the frequency and percentage will be provided.

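### The SAP adds an eligibility condition to ITT and uses that set for safety, departing undeclared from the protocol and leaving any dosed but ineligible subject out of every summary table

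*SAP*

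**What the plan says.** **Protocol 8.3.** ITT covers "the randomized patients who take at least one dose of study medication and have any post-baseline safety data collected", analysed by randomised group. Safety has a wider set: "The safety measures are conducted on the patients who take at least one dose of study medication". Failure of an inclusion or exclusion criterion is the first item in the list of major deviations, and a major deviation removes a subject from PP only.

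**SAP 5.3.1.** The definition becomes: "The INTENT-TO-TREAT (ITT) POPULATION consists of all randomized subjects who receive at least one dose of study medication and fulfill all inclusion, exclusion criteria", with post-baseline safety data required as well. PP again excludes subjects who did not satisfy the inclusion or exclusion criteria.

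**SAP 6.2.** "Two study populations are intention-to-treat (ITT) population and per-protocol (PP) populations which are defined in section 5.3.1". No third set is defined. On use of the sets: "The primary conclusion will be made for the primary endpoint on the ITT population", and "the safety evaluations will be performed on the ITT dataset".

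**SAP 5.4.** "All the statistical analysis will follow protocolized statistical contents". The only departure declared there is that between-arm tests are dropped because the interim did not meet the protocol's requirement and the study was terminated. SAP 5.3 presents the definitions as those planned in the protocol, and the amendment table in SAP section 4 lists no change to populations.

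**The concern.** Two sets are narrowed at once. The first is the set for the primary conclusion, which keeps the ITT label but now drops randomised, treated subjects who failed an eligibility criterion. The second is the safety set, which the protocol defines by exposure alone.

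The safety side matters more. The exclusion criteria in protocol 4.2 include prolonged QTc, suicide risk, pregnancy, unstable medical conditions and clinically significant abnormal laboratory findings. A subject dosed despite one of these is someone whose ECG, C-SSRS or laboratory results a reader would want to see in the summaries. The trial stopped at the interim and no between-arm tests will be run, so descriptive safety tables are a large part of what it will report.

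On efficacy, the decision rule in protocol 8.1 and SAP 5.3.4 compares raw numbers of responders, not proportions. Removing subjects from one arm and not the other therefore shifts the comparison directly.

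**Working it through.** **1. Where a dosed, ineligible subject falls.** Take a subject who was randomised, took at least one dose, has post-baseline safety data, and is later found to have failed an eligibility criterion.

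| Set | Protocol 8.3 | SAP 5.3.1 and 6.2 |
|---|---|---|
| ITT | in | out |
| PP | out | out |
| Safety | in (at least one dose) | out (safety = ITT) |

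Under the protocol the subject is in two of three sets. Under the SAP the subject is in none, and every SAP 6.7 summary omits them.

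**2. A second narrowing of the safety set.** The condition of having any post-baseline safety data is in the protocol's ITT definition too, so it is no conflict for ITT. It is not in the protocol's safety set. Because the SAP uses ITT for safety, a dosed subject without post-baseline data also drops out. This mainly affects denominators, since a subject with a recorded treatment-emergent event has such data.

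**3. How many subjects.** The documents give neither an eligibility-failure rate nor the number actually dosed. Assuming all 69 planned stage I subjects were dosed and failures occur independently at rate r, the expected number is 69r and the chance of at least one is 1 − (1 − r)^69.

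| r (assumed) | Expected number | Chance of at least one |
|---|---|---|
| 2% | 69 × 0.02 = 1.4 | 0.75 |
| 5% | 69 × 0.05 = 3.5 | 0.97 |
| 10% | 69 × 0.10 = 6.9 | 0.999 |

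**4. The plan's own design figures.** Inputs from protocol 8.1: 23 + 10 per arm; response rates 20% and 40%; continue if the responder difference D1 (dose minus placebo) is at least 0; reject the drug if the cumulative difference is below 4; alpha 0.15, power 80%. For one dose against placebo, with exact binomial enumeration of P(D1 ≥ 0 and D1 + D2 ≥ 4):
- at 40% versus 20%: 0.801, against the stated 80%;
- at 20% versus 20%: 0.139, within the stated 0.15.

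The rule has therefore been read as intended.

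**5. Sensitivity of the stage I rule.** Only stage I could have been affected, because the trial ended there. The chance of continuing is P(X − Y ≥ 0), with X ~ Bin(n_dose, p_dose) and Y ~ Bin(n_placebo, 0.20).

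| Subjects lost | From one dose arm only, 40% vs 20% | Same number from both arms, 40% vs 20% | From placebo only, 20% vs 20% |
|---|---|---|---|
| 0 | 0.953 | 0.953 | 0.574 |
| 1 | 0.941 | 0.950 | 0.603 |
| 2 | 0.927 | 0.947 | 0.633 |
| 3 | 0.909 | 0.944 | 0.663 |

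One-sided loss of three costs 0.953 − 0.909 = 0.044 in the chance of continuing with an effective dose. Equal loss costs 0.009.

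**The case against.** **The loss is conditional.** No passage reports a dosed subject who was ineligible, so the number may be zero and the rates above are assumptions. This stands. A reader might infer that adverse events would be lost from the record. The documents do not support that: protocol 8.3 separately requires serious adverse events to be listed with a narrative, without an eligibility restriction, and SAP 8.1 leaves listings to the study report. What is at risk is the summary tables and their denominators.

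**The full two-stage operating characteristics do not apply.** A reader might compute that leaving 20 + 9 subjects in one dose arm against 23 + 10 on placebo cuts power to 0.665, or that the reverse loss raises the false-go rate to 0.193. The arithmetic is right, but both need a stage II that SAP 5.4 shows will not happen. They also put 4 of 33 subjects (12%) out of one arm and none out of the comparator. At independent failure rates of 5% or 10%, four or more failures in a given dose arm with none on placebo has probability of about 1.5% or 1.3%. The figures should not be used.

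**Exclusion on eligibility need not bias the comparison.** Eligibility is assessed at screening, before randomisation, and the trial is double-blind. Excluding subjects on a pre-randomisation fact is not in itself related to treatment. Bias would require violations to be identified with knowledge of treatment or outcome, and nothing in the documents shows that. This stands.

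**Timing.** Because the SAP (version dated April 25, 2024) cites the interim result, a reader might infer that the population was changed in response to it. The documents show only that the SAP came afterwards. They give no reason for the added clause, and do not say which definition the interim used.

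None of this removes the conflict between SAP 5.3.1 and 6.2 and protocol 8.3, or the absence of any declaration in SAP 5.4.

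**Conclusion.** The point holds as an undeclared inconsistency between SAP and protocol in the two sets that carry the primary conclusion and the safety summaries. It rests on the text alone and needs no numerical assumption. Followed as written, the SAP leaves a dosed but ineligible subject in no analysis set.

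The practical size is unknown: about 1, 3 or 7 of 69 planned stage I subjects at assumed rates of 2%, 5% or 10%, and possibly none. The effect on efficacy is secondary. It is confined to the stage I count rule, is at most a few percentage points for an effective dose in the cases examined, and is close to nil if exclusions are balanced. It would matter to the actual decision only if the interim applied the SAP's definition, which the documents do not say.

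The point should be corrected because the SAP claims to follow the protocol and on this point does not.

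**What to change.** 1. In SAP 5.3.1, delete the clause requiring ITT subjects to meet all inclusion and exclusion criteria, so that ITT matches protocol 8.3.
2. Add a safety population of all subjects who took at least one dose, as in protocol 8.3, without the post-baseline-data condition.
3. In SAP 6.2, name three sets and direct the SAP 6.7 safety analyses to the safety population.
4. Keep eligibility violations as a PP exclusion only.

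If the sponsor prefers the narrower ITT, SAP 5.4 should declare and justify it, and the all-dosed safety set is still needed. The study report should also state how many dosed subjects were ineligible, by arm, and which definition the interim used.

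The cost is SAP wording, one population flag and a rerun of the affected tables. The downside is that a few ineligible subjects may re-enter the efficacy set; PP still shows the result without them.

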5.3.2 Endpoints

Primary efficacy endpoint

Improvement of 40% or greater in ADHD Rating Scale-Investigator Rated (ADHD-RS-IR) from baseline up to 8 weeks treatment.

Secondary efficacy endpoints:

The secondary efficacy endpoints	Scales
Symptom remission in ADHD-RS-IV (up to 8 weeks treatment)	– Symptom remission in ADHD Rating Scale-Investigator Rated (ADHD-RS-IV total score \leq 18) score
Score change from baseline (up to 8 weeks treatment)	– ADHD Rating Scale-Investigator Rated (ADHD-RS-IV) score – Conners' Adult Attention-Deficit/Hyperactivity Disorder Rating Scale-Self Report: Short Version (CAARS-S:S) score – Empirical-Sluggish Cognitive Tempo (E-SCT) score
Score change from baseline (of 2 or lower up to 8 weeks treatment)	– Clinical Global Impression - improvement (CGI -I) score

Safety endpoints:

- Change from baseline in:
 - vital sign
 - physical examination
 - electrocardiogram (ECG)
 - laboratory tests (hematology and biochemistry)
- Incidence of Adverse Event (AE)/ Serious Adverse Event (SAE)
- Suicidal ideation and behavior by Columbia-Suicide Severity Rating Scale (C-SSRS)

5.3.3 Statistical Evaluation

Summary statistics will be provided for all efficacy, safety, and baseline/demographic variables. For categorical variables, frequency tables will be presented, including percentages. For continuous variables, descriptive statistics such as number of available observations, mean, median, standard deviation, minimum, and maximum will be tabulated. Baseline characteristics (gender, age, BMI, race) will be summarized for all ITT subjects.

5.3.4 Determination of Sample Size

A two stage design developed by Jung (2008) with significant level $\alpha = 0.15$ and power = 80%.

$$\text{Effect of PDC - 1421 : } \begin{cases} \text{Non-effective , if Response Rate } \leq 20\% \\ \text{Worth further study, if Response Rate } \geq 40\% \end{cases}$$

Stage I	Numbers of responders	Stage II
High-Dose (2 PDC-1421 Capsules) (23 subjects)	$H - P \geq 0$	Add 10 subjects and proceed to stage II
Low-Dose (1 placebo, 1 PDC-1421) (23 subjects)	$L - P \geq 0$	Add 10 subjects and proceed to stage II
Placebo (2 placebo capsules) (23 subjects)		Add 10 subjects and proceed to stage II

If the difference between the accumulated numbers of responders for any PDC-1421 arm and control arm is less than 4, we reject the drug. The minimum sample size required is to recruit 69 subjects, while the maximum sample size is 99.

5.4 Changes in the Conduct of the Study or Planned Analyses

All the statistical analysis will follow protocolized statistical contents. However, due to the interim report results do not meet the requirement of protocol and the study was terminated, the chi-Square test and Wilcoxon signed-rank test between arms will not be performed.

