6.2 Methods and Timing for Assessing, Recording, and

Analyzing of Efficacy Parameters.

The data obtained from eligible subjects before study drug administration in Visit 2 or Visit 1 (if no data at Visit 2) are set as baseline. After the beginning of treatment, the collection of data of efficacy parameters are performed at planned treatment schedule as [section 5.2](#). CRC shall record these data in CRF in detail after each visit during the treatment period. In part II, data comparison between group of 1 capsule TID, 2 capsules TID of PDC-1421 Capsule and 2 capsules TID of placebo will be conducted in final report of this study to evaluate which group(s) of PDC-1421 Capsule are efficient. The rating scales are as follows:

- **ADHD-RS-IV**

The ADHD-RS-IV with Adult Prompts is an 18-item scale base on the DSM-IV-TR' criteria for ADHD that provides a rating of the severity of symptoms¹⁵. The adult prompts serve a guide to explore more fully the extent and severity of ADHD symptoms and create a framework to ascertain impairment. The odd-numbered 9 items assess inattentive symptoms and the even-numbered 9 items assess hyperactive-impulsive symptoms. Scoring is based on a 4-point, yielding a possible total score of 0 – 54. Likert-type severity scale: 0 = Never or Rarely, 1 = Sometimes, 2 = Often, 3 = Very Often. Clinicians should score the highest score that is generated for the

prompts for each item.

For inattention (IA) subscale raw score: Add the odd-numbered 9 items

For hyperactivity-impulsivity (HI) subscale raw score: Add the even-numbered 9 items

To obtain the total raw score: Add the IA and HI subscale raw scores.

- **Clinical Global Impression¹⁶**

At the baseline visit, clinicians completed the CGI-S and were asked to evaluate the severity of subjects' illness with respect to ADHD symptoms based on the clinician's experience with this particular population. Possible scores ranged from 1 (normal, not at all ill) to 7 (among the most extremely ill). At all subsequent study visits, clinicians used the CGI-I to rate the subjects' total improvement based on comparison with their baseline assessment from 1 (very much improved) to 7 (very much worse).

- **CAARS-S:S**

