8.1 Sample Size Determination

In part II, this is a small proof-of-concept study to evaluate low-dosed PDC-1421 arm, high-dosed PDC-1421 arm and placebo arm in the treatment of ADHD. A two stage design developed by Jung (2008) with $\alpha=0.15$ and power=80% will be used. We estimated that the PDC-1421 is considered non-effective if the response rate based on ADHD Rating Scale – Investigator Rated (ADHD-RS-IV) is 20 % or lower and is worth further study if the response rate is 40 % or higher. At the first stage, we recruit 23 subjects for each group. If the difference between the numbers of responders for any PDC-1421 arm and control arm is greater or equal to 0, we proceed to the second stage. We will recruit 10 subjects for each group at the second stage. If the difference between the accumulated numbers of responders for any PDC-1421 arm and control arm is less than 4, we reject the drug. The minimum sample size required is to recruit 69 subjects, while the maximum sample size is 99. No multiple comparison will be applied.

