8.2 Statistical Method

Simple descriptive statistics with 95% confidence interval will be performed with data collected in this study wherever applicable. All data shall be tabulated and presented in the study report. The safety and efficacy data will be analyzed using the non-parametric method wherever appropriate.

The baseline demographic characteristics within each cohort will be compared using chi-square test or exact test for categorical variables and ANOVA (analysis of variance) or Kruskal-Wallis non-parametric ANOVA test for continuous variables. The primary endpoint will be analyzed by chi-square test, while the secondary endpoints will be analyzed using the ANOVA or Kruskal-Wallis non-parametric ANOVA test for continuous endpoints and chi-square test for binary endpoints. Since this is only a small proof-of-concept study, no multiple comparisons will be made to adjust the p-values for all pairwise comparisons.

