6.6 Analysis of Efficacy

6.6.1 Primary Efficacy Endpoint

An improvement of 40% or greater response rate from baseline in treatment group is considered effective and worth further study. The endpoint will be analyzed by checking if the difference of counts of responder is larger than 0 between PDC-1421 arm and placebo arm. Missing data caused by premature termination will be utilized the last observation carried forward (LOCF).

The response rate in the ADHD-RS-IV total score is defined as the following formula.

$$\text{Response rate} = \frac{\text{score}_{\text{visit}} - \text{score}_{\text{baseline}}}{\text{score}_{\text{baseline}}}$$

and the responder is defined as

$$\text{Responder : response rate} \geq 40\%$$

The descriptive statistics will include the proportion of subjects who achieved at least 40% improvement of the ADHD-RS-IV total score at Visit 6 by treatment group and placebo group. The frequency distribution of pre-treatment and post-treatment will also be tabulate and report in bar graph.

The primary measure of efficacy was the ADHD-RS-IV, consisting of 18 items designed to reflect current symptomatology of ADHD based on DSM-IV-TR criteria. Each item is scored on a 4-point scale ranging from 0 (reflecting no symptoms) to 3 (reflecting sever symptoms) with total scores ranging from 0 to 54, which is calculated by summing up scores of subscales. The 18 items may be grouped into 2 subscales:

- For inattention (IA) subscale raw score: Add the odd-numbered 9 items. Higher score indicate severe inattention symptoms.
- For hyperactivity-impulsivity (HI) subscale raw score: Add the even-numbered 9 items. Higher score indicate severe hyperactivity-impulsivity symptoms.
- To obtain the total raw score: Add the IA and HI subscale raw scores.

Following SAS procedures will be applied for chi-Square test between arms.

```
%macro;  
proc freq data = ____;  
    table response*treatment/chisq;  
    output out = chiqtest chisq;  
run;  
%mend;
```

When there has a missing value issue, the following LOCF SAS procedures will be applied.

```
%macro;  
DTAT locf1;  
    LENGTH dtype $15;  
    RETAIN retain;  
    SET lab;  
    BY usubjid visit;  
  
    IF FIRST . visit ^=0 THEN retain = . ;  
    IF qsstresc NE . THEN retain = qsstresc;  
    IF qsstresc= . THEN DO;  
        qsstresclocf = retain;  
        dtype = 'LOCF';  
    END;  
    ELSE qsstresclocf = qsstresc;  
RUN;  
%mend;
```

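### SAP 5.4, written after the failed interim, drops the planned primary test, contradicts SAP 6.6.1, and no confidence interval for a between-arm difference is specified

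*SAP*

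**What the plan says.** - **Planned test.** Protocol 8.2: "The primary endpoint will be analyzed by chi-square test". The same section plans ANOVA or Kruskal-Wallis for continuous secondary endpoints, chi-square for binary ones, and 95% confidence intervals wherever they apply. Protocol 6.2 gives the purpose of the three-arm comparison: "to evaluate which group(s) of PDC-1421 Capsule are efficient".
- **Design.** Protocol 8.1 uses a two-stage rule on responder counts with alpha 0.15 and 80% power. Stage I: "At the first stage, we recruit 23 subjects for each group". The trial continues if the drug-minus-placebo count is 0 or more for any PDC-1421 arm. After stage II, the condition for failure reads: "difference between the accumulated numbers of responders for any PDC-1421 arm and control arm is less than 4, we reject the drug".
- **Change.** SAP 5.4 says that analyses follow the protocol. It then says that, because the interim result fell short and the study was terminated, "the chi-Square test and Wilcoxon signed-rank test between arms will not be performed". The only SAP version listed in 8.2 was approved on April 25, 2024.
- **Still in the SAP.** Section 6.6.1 compares responder counts between drug and placebo arms, gives the Visit 6 responder proportion by group, and states: "Following SAS procedures will be applied for chi-Square test between arms". Section 6.6.2 makes the secondary endpoints descriptive. Section 6.2 provides a 95% interval for means, but only frequency and percentage for categorical variables.

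**The concern.** The primary test was withdrawn in a document that already reports the interim outcome and gives that outcome as its reason. Three faults follow.

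1. The SAP gives opposite instructions for the primary test in 5.4 and 6.6.1, so a programmer cannot tell which applies.
2. One of the two cancelled tests was never planned. A signed-rank test compares paired values and cannot compare independent arms. The tests that the protocol did plan for the scales, ANOVA or Kruskal-Wallis, are not named in 5.4, so their status is unclear.
3. With the test gone, nothing specified replaces it as a measure of uncertainty for the primary endpoint.

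What is at stake is what can be learned from the 69 stage I subjects. A futility stop on counts gives a direction. It does not tell a reader which benefits the data still allow at each dose.

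**Working it through.** **Inputs.** Protocol 8.1 gives alpha 0.15, power 80%, 23 then 10 subjects per arm, a stage I bound of 0 and a final bound of 4. The drug "is 20 % or lower and is worth further study if the response rate is 40 % or higher". Two assumptions are needed: 20% is also the placebo rate, which makes the planned benefit 40 − 20 = 20 points, and the rule is one-sided, because it counts only an excess on drug.

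**The plan's own figure.** For one dose against placebo, let D1 be the difference of two Bin(23, p) counts and D2 the difference of two Bin(10, p) counts. Success is D1 ≥ 0 and D1 + D2 ≥ 4. Exact results:
- 20% v 20%: 0.139, within the stated 0.15.
- 40% v 20%: 0.801, matching the stated 80%.

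The count rule is therefore sound per comparison and can remain the decision.

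**What a stage I stop conveys.** For one dose, P(D1 < 0) is 42.6% at 20% v 20% and 4.7% at 40% v 20%. Both doses fall below placebo with probability Σx P(placebo = x) × P(drug < x)², the sum running over placebo counts x from 0 to 23. This is about 27% if all three rates are 20%, and about 1% if both doses are at 40%. The stop is evidence against both doses reaching 40%, but it gives no effect size for either.

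**What an interval would add.** The observed counts are not in the documents, so assumed counts out of 23 per arm are used, each of which fails the ≥ 0 rule. Newcombe interval, with d = p1 − p2 (drug minus placebo) and Wilson limits (l, u) for each arm:
- lower = d − √[(p1 − l1)² + (u2 − p2)²]
- upper = d + √[(u1 − p1)² + (p2 − l2)²]

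Example, 4 v 5, in percentage points: p1 = 17.39 with Wilson limits 6.98 to 37.14; p2 = 21.74 with limits 9.66 to 41.90; d = −4.35.
- upper = −4.35 + √(19.75² + 12.08²) = −4.35 + 23.15 = +18.8
- lower = −4.35 − √(10.41² + 20.16²) = −4.35 − 22.69 = −27.0

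| Drug v placebo responders (of 23) | Difference | 95% lower | 95% upper | 20 points excluded? |
|---|---|---|---|---|
| 3 v 4 | −4.3 | −25.9 | +17.4 | yes |
| 4 v 5 | −4.3 | −27.0 | +18.8 | yes |
| 6 v 7 | −4.3 | −28.9 | +20.9 | no |
| 10 v 11 | −4.3 | −30.6 | +22.7 | no |
| 3 v 8 | −21.7 | −43.8 | +3.1 | yes |

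The first four rows have the same count difference, so the count comparison cannot tell them apart, yet they differ on whether the planned benefit is excluded.

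**The case against.** The strongest reply is that the change is disclosed, with its reason, in the section meant for changes. After a futility stop, leaving out a test cannot create a false positive. The statistic that the design decides on is kept in 6.6.1, and dividing the count difference by the arm size gives the point difference. The protocol's promise of confidence intervals is not revoked, and 5.4 says that the protocol is followed. All of this stands, and it limits the point to estimation and consistency.

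Stronger readings that a reader might infer are not supported:
- **That every between-arm comparison was cancelled, or that no effect estimate remains.** Section 5.4 names two tests. The count comparison and per-arm proportions remain; what is missing is a specified difference with its interval.
- **That the SAP authors acted on unblinded data.** The text shows that they knew the interim had failed. Protocol 3.4 restricts interim unblinding to the CRO, and nothing says that the authors saw arm-level results.
- **That a 20-point benefit is certainly still open.** A tie such as 5 v 5 would suggest so, but a tie satisfies the ≥ 0 rule in Protocol 8.1 and SAP 5.3.4 and would have led to stage II. Only the looser wording of 6.6.1 (larger than 0) would stop on a tie; that wording should be aligned. Among counts that do fail the ≥ 0 rule, some exclude 20 points and some do not.
- **That the chi-square was badly underpowered by design.** That needs a two-sided 5% level, which the plan never sets. At two-sided 0.30, equivalent to the design's one-sided 0.15, exact chi-square power at 33 per arm is about 79%, close to the stated 80%.

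**Conclusion.** The point holds as a contradiction within the SAP and an omission that is cheap to repair. Sections 5.4 and 6.6.1 cannot both be followed, the signed-rank test named in 5.4 was not in the protocol, and the SAP specifies no interval for the primary between-arm difference, although the protocol promises intervals wherever they apply.

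The size is a matter of precision. With one fewer responder on drug, the upper limits shown run from +17.4 to +22.7 points, on either side of the planned 20; a clearly worse arm (3 v 8) gives +3.1. The figures assume 23 analysed per arm, a 20% placebo rate for the planned benefit, a stop under the ≥ 0 rule, and illustrative counts. The decision to stop is not in question.

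**What to change.** 1. Reconcile SAP 5.4 with 6.6.1 so that the status of the chi-square is stated once, with the reason and the fact that the interim outcome was known.
2. Remove the signed-rank wording, and state what happens to the planned ANOVA or Kruskal-Wallis analyses.
3. For each dose against placebo, report the difference in Visit 6 responder proportion with a 95% score-based interval, such as Newcombe. For the scales, report mean differences with 95% intervals.
4. Label these results supportive, stage I only, after early stopping. A fixed-sample interval takes no account of the stop, and estimates from trials stopped for low counts tend to understate the effect. The two-stage count rule stays the decision.
5. Align the larger-than-0 wording in 6.6.1 with the ≥ 0 rule in Protocol 8.1 and SAP 5.3.4.

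The cost is a few extra tables and no new data. The one downside is that the intervals will be wide, which is an accurate account of what 23 per arm can show.
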